8.6.7 Pregnancy Tests

Dates and results of pregnancy tests will be listed within Safety Analysis Set.

8.6.8 ECOG Performance Status

Shift from baseline ECOG to worst on-study ECOG will be summarized. Listing will be provided for Safety Analysis Set.

8.7 Efficacy Analysis

All efficacy analyses will be performed based on the Safety Analysis Set and the Efficacy Analysis Set.

8.7.1 Best Overall Response and Objective Response per RECIST 1.1

Best overall response (BOR) will be derived from time-point RECIST 1.1 assessments by investigators. In the primary analysis, BOR will be evaluated over all on-study time-point assessments recorded before start of a new anti-cancer therapy, in consideration of RECIST 1.1 definition: "The best overall response is the best response recorded from the start of the study

Confidential Page 26 of 30

Statistical Analysis Plan 07 Oct 2021

treatment until the end of treatment taking into account any requirement for confirmation. On occasion a response may not be documented until after the end of therapy so protocols should be clear if post-treatment assessments are to be considered in determination of best overall response" (Eisenhauer et al 2009). Since all assessments are considered for BOR, the confirmed objective response or stable disease (SD) may occur after a transient time-point progressive disease (PD) assessment(s).

In the secondary analysis, conducted for sensitivity evaluation, an alternative, more conservative approach will be used. BOR will be evaluated only over time-point assessments until first observed PD, as initially proposed in RECIST 1.0 (Therasse et al 2000).

Confirmation of objective response (complete response [CR] or partial response [PR]) is required for respective BOR of CR or PR. Confirmation must be obtained at a subsequent assessment at least 4 weeks apart. In case of CR, the confirmatory assessment must be performed at a consecutive assessment, except for intercurrent non-evaluable assessments.

In case of PR, confirmatory assessment after initial CR/PR may be obtained a) in the primary analysis any time at least 4 weeks apart from the initial assessment, without restrictions on intercurrent assessment b) in the secondary analysis, any time after 4 weeks and after at most 1 intercurrent assessment of non-evaluable (NE) or SD.

For patients who did not fulfill requirements for BOR of CR or PR as described above, BOR of SD is defined, in the primary analysis, as i) initial time point assessment(s) of SD, PR, CR without PD at a minimum interval of 39 days (6 weeks-3 days), disregarding NE assessments and/or ii) unconfirmed PR or CR any time at initial evaluation, without PD at a minimum interval of 39 days and/or iii) durable SD following transient PD: at least 2 assessment(s) of SD, PR, CR (ignoring intercurrent NE assessments) at least 39 days (6 weeks-3 days) apart and without new PD within 84 days, counting time from the last transient PD assessment. Subjects who have a response of PR or CR with no subsequent tumor assessments will be assigned a BOR of SD and will be flagged in listings. In the secondary analysis, BOR evaluation of SD is only considered based on only criterion i) above. For BOR of SD without confirmation, the stable disease must meet the criterion of minimum time of 39 days.

For patients with time point assessment(s) of PD, excluding any transient PDs (PD followed by confirmed objective response or durable SD) and who do not satisfy criteria for BOR of CR, PR, and SD described above, the BOR assessments in the primary analysis will be PD. In the secondary analysis, a similar definition will be used but without excluding transient PDs.

Finally, BOR of NE will be assigned where there are either no evaluable time point assessments at all or first time point assessment(s) of SD was before minimum interval of 39 days without evaluable assessments preformed after 39 days.

The objective response rate (ORR) is the percentage of subjects with a BOR of PR or CR (i.e., objective response). The analysis of ORR will include confirmed responses and unconfirmed responses for both primary and alternative analyses. Subjects with missing tumor response status assessment will be counted as non-response (that is, subjects without any follow-up assessment) will be counted in the denominator for ORR.

BOR and ORR will be listed for Safety Analysis Set as available using primary and alternative definitions. For confirmed response, duration of response will be listed (see Section 8.7.2). The listings of time-point response will include assessments of target lesion, non-target lesions, and

Confidential Page 27 of 30

new lesion data, as well as percentage change from baseline in the sum of diameters of target lesions.

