8.7.2 Duration of Response

Duration of response (DOR) will be analyzed only for subjects who responded to the study treatment. DOR is defined as the time from first observation of CR or PR which was subsequently confirmed until the first time of disease progression or death by any cause within 90 days (i.e., 12 weeks+6 days) of last tumor assessment. All assessments performed before initiation of a new anti-cancer therapy will considered for evaluation of DOR. If a patient transitioned to a new anti-cancer therapy, any time point assessment(s) and death(s) that happened after that will be disregarded. Similar to evaluation of BOR, in the primary analysis any transient time-point PD(s) will be disregarded for determination of DOR when followed by confirmed objective response or durable stable disease, as defined in Section 8.7.1. In the alternative (sensitivity) analysis, DOR will be counted using the date of first observed PD, whether transient or not.

The starting event for DOR will be the date of the first objective response. The terminating event will be the date of PD or death within 90 days (i.e., 12 weeks+6 days) of the last tumor assessment, whichever occurs first. The censoring event will be the earliest of the dates of last evaluable assessment, last evaluable assessment performed before initiation of new anti-cancer therapy (if applicable), or last evaluable assessment without any assessment in the following 90 days and then followed by PD or death.

DOR will be reported in months and summarized by quartiles estimated from Kaplan-Meier curve, as well as Kaplan-Meier estimates at 6, 9, 12, 18 months. Number and percent of censored and non-censored observations and a plot Kaplan-Meier curve will be provided.

In addition, duration of observation of DOR (whether censored or not) will be summarized as "Observed DOR". The shortest and longest observations will be provided with censoring indicator.

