8.7.3 Disease Control Rate

Disease control rate (DCR) is defined as proportion of subjects who have a confirmed response (CR or PR) or SD without PD within 81 days (12 weeks – 3 days) at study start, or durable SD following PD. In the alternative analysis, used for sensitivity analysis in parallel with alternative algorithm for BOR, described previously it is defined as proportion of subjects who have a confirmed response (CR or PR) or SD without PD within 81 days at study start.

DCR and number of subjects with disease control will be tabulated.

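### SAP 8.7.1 gives ORR two different numerators: one built on confirmed BOR of CR or PR, the other also taking in unconfirmed responses

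*SAP*

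**What the plan says.** SAP Section 8.7.1 builds ORR up from BOR.

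- **Confirmation.** "Confirmation of objective response (complete response [CR] or partial response [PR]) is required for respective BOR of CR or PR". On timing: "Confirmation must be obtained at a subsequent assessment at least 4 weeks apart".
- **Unconfirmed responses.** Where no scan follows the response, the rule is: "Subjects who have a response of PR or CR with no subsequent tumor assessments will be assigned a BOR of SD". Criterion ii for a BOR of SD in the primary analysis also covers "unconfirmed PR or CR any time at initial evaluation, without PD at a minimum interval of 39 days".
- **ORR definition.** "The objective response rate (ORR) is the percentage of subjects with a BOR of PR or CR (i.e., objective response".
- **The sentence that follows it.** "The analysis of ORR will include confirmed responses and unconfirmed responses for both primary and alternative analyses".

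The neighbouring endpoints use confirmed responses. In SAP Section 8.7.2, "DOR is defined as the time from first observation of CR or PR which was subsequently confirmed". In SAP Section 8.7.3, DCR is the "proportion of subjects who have a confirmed response (CR or PR) or SD without PD within 81 days" from study start; the primary version also admits durable SD after PD.

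Protocol Section 6.2.1.2 defines ORR through CR or PR under RECIST 1.1 and does not mention confirmation. Protocol Section 6.4.2.3 and the criteria reproduced in Appendix E add no response-confirmation rule. SAP Section 5.1 declares no change from the protocol's planned analysis.

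**The concern.** Two programmers who each follow one of the adjacent sentences would produce different ORRs from the same data, and both could point to the plan. The alternative analysis does not settle the matter. It is presented as the more conservative version, yet the disputed sentence covers it too.

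This matters because the trial is open-label and non-randomized, response is assessed by the investigator, and ORR is one of the main descriptions of activity. If the numerator is not fixed in advance, the rule can be chosen after the responses have been seen. A reader of the report could also find an ORR that does not match the BOR table or the number of subjects contributing to DOR, with nothing in the SAP to explain the gap.

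**Working it through.** The documents state no ORR, target rate or expected response count, so there is no figure to reproduce. The check compares the rules and then works out the effect per subject.

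**Step 1: what each sentence implies.** Let c be the number of subjects with a confirmed CR or PR, u the number with only unconfirmed CR or PR, and n the analysis set.

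- By the definition, the numerator is BOR of CR or PR. Confirmation is required for that, so ORR = c/n.
- By the next sentence, read as one pooled rate, ORR = (c + u)/n.
- The difference is u/n, which is never negative because n is the same in both.

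**Step 2: agreement with other outputs under the pooled reading.**

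- The BOR table shows c subjects with CR or PR, while ORR counts c + u.
- DOR includes c subjects, so the ORR numerator exceeds it by u.
- The primary and alternative analyses differ in how they treat scans after PD and which sequences confirm a PR. If unconfirmed responses count anyway, the confirmation sequence no longer affects ORR.

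**Step 3: a subject at the extreme.** Suppose PD at Week 6, PR at Week 12 and PD at Week 18, with treatment continued beyond progression and 6-weekly imaging as Protocol Section 3.7 allows. In the primary BOR analysis:

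- The PR is not confirmed, so BOR is not CR or PR.
- The initial assessment is PD, so SD criteria i and ii are not met.
- There is only one non-PD assessment after the first PD, so SD criterion iii, which needs at least two, is not met.
- BOR is therefore PD, and the subject fails DCR.

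If unconfirmed responses count, this subject is still a responder in the primary ORR. The SAP gives no derivation rule that would exclude the case.

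**Step 4: size per subject.** Planned sizes are from SAP Section 3.2: up to 60 in Phase 2, about 40 non-HCC and about 20 HCC. Each unconfirmed responder adds 100/n percentage points:

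- n=60: 100/60 = 1.67
- n=40: 100/40 = 2.5
- n=20: 100/20 = 5.0

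**Step 5: illustration with assumed counts.** SAP Section 8.1 specifies two-sided 95% Wilson intervals. With p = x/n and z = 1.96, the centre is (p + z²/2n)/(1 + z²/n) and the half-width is z·√[p(1−p)/n + z²/4n²]/(1 + z²/n). For 3/60 the centre is 0.0820/1.0640 = 0.0771 and the half-width is 1.96 × 0.03253/1.0640 = 0.0599, giving 1.7% to 13.7%.

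| Assumed confirmed / n | u = 0 | u = 1 | u = 2 | u = 3 |
|---|---|---|---|---|
| 3 / 60 | 5.0% (1.7–13.7) | 6.7% (2.6–15.9) | 8.3% (3.6–18.1) | 10.0% (4.7–20.1) |
| 2 / 40 | 5.0% (1.4–16.5) | 7.5% (2.6–19.9) | 10.0% (4.0–23.1) | 12.5% (5.5–26.1) |
| 2 / 20 | 10.0% (2.8–30.1) | 15.0% (5.2–36.0) | 20.0% (8.1–41.6) | 25.0% (11.2–46.9) |

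All the response counts are assumptions. Only the direction and the points per subject follow from the documents.

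**The case against.** The strongest reply is that the sentence announces two rates, one confirmed and one including unconfirmed responses, and not a single pooled numerator. Nearby text fits this: the SAP lists duration only for confirmed responses, and it flags responders who have no later scan. That reading is possible, and pooling is not proven to be the intent. But the SAP labels no second rate, does not say which is the main one, and gives no rule for deriving the second. The labels primary and alternative are already used for a different distinction. The sentence needs rewriting on either reading.

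A second reply is that counting unconfirmed responses is no departure from the protocol, whose ORR definition has no confirmation rule. This stands. A reader might infer that the protocol endpoint is being inflated, but the documents do not support that. The possible rise is measured against the SAP's own definition only.

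Third, ORR is secondary, serves a preliminary look at efficacy, and has no hypothesis test; the sample sizes are not based on inferential statistics. This also stands and limits the severity.

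**Conclusion.** The contradiction is in the current SAP text and should be fixed. A BOR of CR or PR needs confirmation, ORR is defined from that BOR, and the next sentence brings unconfirmed responses into both ORR analyses. If they are pooled, ORR stays the same or rises by 1.67, 2.5 or 5 percentage points per added subject at n=60, 40 or 20. How many subjects would be added is unknown. The sizes assume planned enrolment is met. No type I error, power or decision rule is affected.

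Two stronger readings go beyond the documents:

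- A reader might infer that every unconfirmed response becomes SD. Only the rule for subjects with no later scan is unconditional. The other SD criteria carry conditions on timing and PD, and a subject who misses them can have a BOR of PD.
- A reader might infer that the BOR, DOR and DCR tables all conflict. Those three rest on confirmed response and remain consistent with one another. Some unconfirmed responders also still count in DCR through SD. The ORR sentence is the one out of line.

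**What to change.** Replace the sentence in SAP Section 8.7.1 with:

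> The primary and alternative ORR count only confirmed CR/PR (BOR of CR or PR). A rate that also includes unconfirmed CR/PR is reported as a separately labelled supportive summary, counting subjects with at least one time-point CR/PR before new anti-cancer therapy (and, in the alternative analysis, before first PD).

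In SAP Section 5.1, replace the statement that nothing has changed with a note that the SAP adds a confirmation requirement to the protocol's ORR definition. Section 6 of the protocol lets the SAP modify its plans and calls for an amendment only for major changes to the primary endpoint or its analysis, so this change to a secondary endpoint can be made in the SAP alone.

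The cost is one replaced sentence, one entry in Section 5.1 and one labelled summary, with no new data. The downside is that the reported ORR may be slightly lower than under a pooled count. The change should be made before the final analysis.

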8.7.2 Duration of Response

Duration of response (DOR) will be analyzed only for subjects who responded to the study treatment. DOR is defined as the time from first observation of CR or PR which was subsequently confirmed until the first time of disease progression or death by any cause within 90 days (i.e., 12 weeks+6 days) of last tumor assessment. All assessments performed before initiation of a new anti-cancer therapy will considered for evaluation of DOR. If a patient transitioned to a new anti-cancer therapy, any time point assessment(s) and death(s) that happened after that will be disregarded. Similar to evaluation of BOR, in the primary analysis any transient time-point PD(s) will be disregarded for determination of DOR when followed by confirmed objective response or durable stable disease, as defined in Section 8.7.1. In the alternative (sensitivity) analysis, DOR will be counted using the date of first observed PD, whether transient or not.

The starting event for DOR will be the date of the first objective response. The terminating event will be the date of PD or death within 90 days (i.e., 12 weeks+6 days) of the last tumor assessment, whichever occurs first. The censoring event will be the earliest of the dates of last evaluable assessment, last evaluable assessment performed before initiation of new anti-cancer therapy (if applicable), or last evaluable assessment without any assessment in the following 90 days and then followed by PD or death.

DOR will be reported in months and summarized by quartiles estimated from Kaplan-Meier curve, as well as Kaplan-Meier estimates at 6, 9, 12, 18 months. Number and percent of censored and non-censored observations and a plot Kaplan-Meier curve will be provided.

In addition, duration of observation of DOR (whether censored or not) will be summarized as "Observed DOR". The shortest and longest observations will be provided with censoring indicator.

8.7.3 Disease Control Rate

Disease control rate (DCR) is defined as proportion of subjects who have a confirmed response (CR or PR) or SD without PD within 81 days (12 weeks – 3 days) at study start, or durable SD following PD. In the alternative analysis, used for sensitivity analysis in parallel with alternative algorithm for BOR, described previously it is defined as proportion of subjects who have a confirmed response (CR or PR) or SD without PD within 81 days at study start.

DCR and number of subjects with disease control will be tabulated.

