6.2.1.2 Secondary Endpoints

- Objective response rate, (ORR), defined as the percentage of subjects having CR or PR, as determined by radiographic disease assessments per RECIST 1.1.
- Disease control rate (DCR) will include subjects that have best overall response (BOR) of CR, PR and SD for at least 12 weeks.
- Progression-free survival (PFS), defined as the interval from the date of first dose of investigational agent until the earliest date of disease progression, as determined by investigator assessment of objective radiographic disease assessments per RECIST 1,1, or death due to any cause if occurring sooner than progression.
- Duration of response, (DOR), defined as the interval from the date measurement criteria are met for CR or PR (whichever is first recorded) until the earliest date of disease progression, as determined by investigator assessment of objective radiographic disease assessments per RECIST 1.1, or death due to any cause if occurring sooner than progression. Only subjects who achieve an initial response will be evaluated for DOR.
- Overall survival (OS), defined as the interval from the date of first dose of investigational agent until the date of death.
- The pharmacologically active dose of AGEN1884, determined through clinical signs of drug activity, surrogate markers, and pharmacodynamic studies, including but not limited to the presence of irAEs.

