4.5 Secondary Endpoints

- Objective response rate, (ORR), defined as the percentage of subjects having complete response (CR) or partial response (PR), as determined by radiographic disease assessments per RECIST 1.1.
- Disease control rate (DCR) will include subjects that have best overall response (BOR) of CR, PR and stable disease (SD) for at least 12 weeks.
- Progression-free survival (PFS), defined as the interval from the date of first dose of investigational agent until the earliest date of disease progression (PD), as determined by investigator assessment of objective radiographic disease assessments per RECIST 1.1, or death due to any cause if occurring sooner than progression.
- Duration of response, (DOR), defined as the interval from the date measurement criteria are met for CR or PR (whichever is first recorded) until the earliest date of disease progression, as determined by investigator assessment of objective radiographic disease assessments per RECIST 1.1, or death due to any cause if occurring sooner than progression. Only subjects who achieve an initial response will be evaluated for DOR.
- Overall survival (OS), defined as the interval from the date of first dose of investigational agent until the date of death.
- The pharmacologically active dose of AGEN1884, determined through clinical signs of drug activity, surrogate markers, or pharmacodynamic studies, including but not limited to the presence of immune-related adverse events.

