5 PLANNED ANALYSIS

5.1 Summary of Changes to the Planned Statistical Analysis Described in the Protocol

None.

Confidential Page 12 of 30

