8.7.6 Progression-Free Survival

Progression-free survival (PFS) is defined as the interval from the date of first dose of investigational agent until the earliest date of PD per RECIST 1.1 or death due to any cause within 90 days (i.e., 12 weeks+6 days) of last tumor assessment (if no progression is documented). If a patient transitioned to a new anti-cancer therapy, any time point assessment(s) and death(s) that happened after that will be disregarded.

The primary analysis will be performed ignoring transient PDs, using the same definition of transient PDs as in Section 8.7.1. Thus, the terminating event will be a non-transient PD or death, whichever occurs first. Patients who did not experience a non-transient PD or death will be censored on the date of last evaluable tumor assessment, the date of the last evaluable assessment without any assessment in the following 90 days and then followed by PD or death, or the last evaluable assessment performed before initiation of new anti-cancer therapy (if applicable), whichever comes earlier.

The alternative (sensitivity) analysis will be performed for terminating event of death or first observed time-point PD, whichever occurs first. Censoring will be on the date of last evaluable tumor assessment, the date of the last evaluable assessment without any assessment in the following 90 days and then followed by PD or death, or the last evaluable assessment performed before initiation of new anti-cancer therapy (if applicable), whichever occurs first.

PFS will be reported in months. Median PFS will be provided (estimated using K-M estimate, with 95% CI) and Kaplan-Meier curves of PFS will be plotted.

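### SAP 8.7.3 does not implement disease control as 12 weeks of stable disease: it requires no scan near Week 12 and does not count an early death as failure

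*SAP*

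**What the plan says.** The endpoint is worded the same way in both documents. Protocol 6.2.1.2 has "BOR) of CR, PR and SD for at least 12 weeks", and SAP 4.5 has "PR and stable disease (SD) for at least 12 weeks". SAP 5.1, titled "Summary of Changes to the Planned Statistical Analysis Described in the Protocol", answers None.

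The operative rule is in SAP 8.7.3. The primary analysis takes the "proportion of subjects who have a confirmed response (CR or PR) or SD without PD within 81 days" from study start, and adds durable SD following PD. The alternative analysis drops the durable-SD route but keeps the same 81-day wording.

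Three other SAP rules bear on this:

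- **BOR of SD (8.7.1).** The ordinary route is "initial time point assessment(s) of SD, PR, CR without PD at a minimum interval of 39 days". A PR or CR with no later assessment is also assigned SD.
- **Evaluability (8.7.1).** NE is assigned when the "first time point assessment(s) of SD was before minimum interval of 39 days without evaluable assessments preformed after 39 days". Durable SD after a transient PD needs "at least 2 assessment(s) of SD, PR, CR (ignoring intercurrent NE assessments) at least 39 days (6 weeks-3 days) apart".
- **Death (8.7.6).** PFS counts "death due to any cause within 90 days (i.e., 12 weeks+6 days) of last tumor assessment" as an event. DOR (8.7.2) also names death as a terminating event.

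**The concern.** Not having observed PD by Day 81 is different from having had stable disease for 12 weeks. A subject can be free of observed PD because the disease was stable, because nobody looked, or because the subject died first. SAP 8.7.3 does not separate these.

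The SAP deals with the same problem elsewhere. It has an NE rule at 39 days, a two-assessment rule for durable SD, and a death rule for PFS and DOR. The initial-SD route to disease control has none of these at 81 days. The missing-assessment rule in 8.7.1 is written for ORR and covers only subjects with no follow-up assessment at all.

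The result is that a subject who died before Week 12, or was never evaluably scanned near it, can be reported as having 12-week disease control. DCR is also reported by subgroup (SAP 8.7.5), including HCC with about 20 subjects, where one subject is visible in the rate.

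**Working it through.** **Inputs.** 3-week cycles for the first 4 cycles (Protocol 4.1.1). Scan at C3D1 ±3 days and at C4D15 ±2 days (Protocol Table 10). 39-, 81- and 90-day limits (SAP 8.7.1, 8.7.3, 8.7.6). Conversion factor 30.4375 days per month and Wilson intervals (SAP 8.1). Phase 2 N up to 60, about 20 HCC and 40 non-HCC (SAP 3.2).

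**The SAP's own limits reproduce.** 6×7 − 3 = 39; 12×7 − 3 = 81; 12×7 + 6 = 90.

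**Scan days, with first dose as Day 1.** C3D1 = 1 + 2×21 = 43 (window 40–46). C4D15 = 1 + 3×21 + 14 = 78 (window 76–80). So one on-schedule scan at C3D1 satisfies the 39-day minimum, and the whole Week-12 window closes before Day 81.

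**Literal application of 8.7.3 to hypothetical histories**, beside a rule that also needs a non-PD scan on or after Day 76, before any PD, and no death within 81 days:

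| History | SAP 8.7.3 | With added rule |
|---|---|---|
| SD Day 43, death Day 60 | controlled | not controlled |
| SD Day 43, no later scan | controlled | not controlled |
| SD Day 43, NE Day 78 | controlled | not controlled |
| SD Day 43, PD Day 78 | not controlled | not controlled |
| SD Days 43 and 78, PD Day 120 | controlled | controlled |
| SD Days 43 and 84 | controlled | controlled |
| SD Day 43, first PD Day 85 | controlled | not controlled |

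The first three rows are the defect: the only documented SD is at about 6 weeks. The alternative analysis gives the same answers, because its 81-day wording is the same.

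**Comparison with PFS.** For the death on Day 60, the gap from the last scan is 60 − 43 = 17 days, within 90, so it is a PFS event at 60/30.4375 = 1.97 months. Twelve weeks is 84/30.4375 = 2.76 months. The same subject fails PFS before 12 weeks and succeeds on DCR. The subject with no later scan, PD or death is simply censored for PFS at Day 43, so there the two analyses do not contradict each other.

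**Size per subject.** 1/60 = 1.7 points; 1/40 = 2.5 points; 1/20 = 5.0 points.

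**Illustration.** Both the base rates and the counts are assumptions; neither is in the documents. 95% Wilson intervals in brackets.

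- n=20, base 25%: 5/20 = 25.0% (11.2–46.9); one extra gives 6/20 = 30.0% (14.5–51.9); three extra give 8/20 = 40.0% (21.9–61.3).
- n=20, base 30%: 6/20 = 30.0% (14.5–51.9); one extra gives 7/20 = 35.0% (18.1–56.7).
- N=60, base 25%: 15/60 = 25.0% (15.8–37.2); one extra gives 16/60 = 26.7% (17.1–39.0); three extra give 18/60 = 30.0% (19.9–42.5).

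**The case against.** The best defence is that 8.7.3 should be read with SAP 4.5. The endpoint there is 12 weeks of SD, and 81 days is 12 weeks with a 3-day allowance, just as 39 is 6 weeks with the same allowance. On that reading 8.7.3 only adds a window, and nobody would count a death on Day 60 as disease control. This probably is the intent. It still gives a programmer no rule: neither section says which scan establishes the 12 weeks, or what happens when it is missing or the subject has died.

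The 3-day allowance is ordinary windowing and is not at fault. The entry None in SAP 5.1 carries little weight alone, since Protocol section 6 lets the SAP modify the protocol's plans.

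A reader might infer that subjects who start new therapy and then progress before Day 81 are also credited. The text does not support this. PD on Day 78 is PD within 81 days and fails under 8.7.3 as written. It would be credited only if the new-therapy cut-off for BOR in 8.7.1 were carried into DCR, which 8.7.3 does not say.

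It is also fair that DCR is descriptive, that no decision rule uses it, that the study is not sized on inference, and that time-point responses are listed, so affected subjects can be traced. These points limit the weight of the finding but do not remove it.

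**Conclusion.** The point holds. As written, SAP 8.7.3 gives a result contrary to the endpoint in Protocol 6.2.1.2 and SAP 4.5 for subjects whose only SD is early and who then die or have no later evaluable scan. It does so in both analyses. For the early death it also contradicts the SAP's own PFS analysis.

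The only size that follows from the documents is per subject: 1.7 points at N=60 and 5.0 points at n=20. A reader might infer that the reported DCR will be materially inflated. The documents do not support that, because they give neither the number of such subjects nor a base rate, and the illustrative intervals overlap heavily. Confirmed CR and PR are unaffected. This should be corrected, but it does not threaten the primary objectives.

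**What to change.** In SAP 8.7.3, for both analyses, keep the condition of no PD within 81 days and add:

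> SD counts only if there is an evaluable CR, PR or SD assessment, scheduled or unscheduled, on or after Day 76 (lower limit of the Table 10 Week-12 window, Day 78 ± 2), obtained before any PD and before any new anti-cancer therapy, and the subject did not die within 81 days. All others count as not controlled and stay in the denominator.

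The words 'before any PD' are needed. Without them, SD on Day 43, first PD on Day 85 and a single SD on Day 127 would qualify, although the two-assessment rule for durable SD is not met. Day 76 is preferred to Day 81 because an on-schedule Week-12 scan falls on Days 76–80 and would otherwise not count.

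Keep the confirmed-response route in both analyses. In the primary analysis only, keep durable SD following PD as its own route under the 8.7.1 criteria, and add no death within its 84-day period. Tabulate 'not controlled' by reason: PD, death, new therapy, no evaluable scan on or after Day 76.

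**Cost.** SAP text and derivation code. No new data are needed, since SAP 6.5 already admits unscheduled and out-of-window scans.

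**Downsides.** DCR may be slightly lower. A subject whose late Week-12 scan first shows PD (for example on Day 85) counts as not controlled. A subject off drug without PD may have no scan due near Day 76, because Protocol 3.5 (every 12 weeks) and Protocol 5.7.1 (every 6 weeks or a disease-specific schedule) differ. That subject would also count as not controlled. The two protocol sections should be reconciled, and the by-reason table will show how many subjects are affected. Day 76 is a choice tied to the Table 10 window and should be stated as such.
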